## Abstract

**BACKGROUND:** Cardiovascular disease (CVD) is the leading cause of mortality among Veterans, and suboptimal risk factor control is an important mechanism for the continued prevalence of CVD. Despite clinic based programming that includes nurse care management, pharmacy support, telephone care programs and intensive quality improvement efforts, CVD risk factors remain sub-optimally controlled among Veterans. Given the high prevalence and cost CVD within the Department of Veterans Affairs, cost-effective mechanisms are needed to manage the burden of prevalent CVD risk factors. Veteran peer health coaches may be one such mechanism; however, previous work has provided limited data of this model with VHA primary care. Previous studies of peer support in non-VHA populations report significant improvement in hypertension control and CVD risk reduction.

**OBJECTIVES:** The proposed project will test the effectiveness of **Vet-COACH** (**V**eteran peer **C**oaches **O**ptimizing and **A**dvancing **C**ardiac **H**ealth), a peer health coaching program to help reduce CVD risk among Veterans. The overall goal of this study is to test the effectiveness of a peer health coach intervention to promote health behavior change among Veterans with multiple CVD risk factors with a hybrid type 1 implementation study. To target a high risk population, we will focus on Veterans with poorly controlled hypertension and at least one other CVD risk factor.

**METHODS:** We will conduct a randomized controlled trial that will enroll n=400 Veterans to compare a peer health coach intervention consisting of telephone support, and linkages to appropriate community-based and clinic resources compared to usual VHA primary care. The primary outcome is reduction in systolic blood pressure from baseline to follow-up at 1-year. Secondary outcomes include a reduction in Framingham Cardiovascular risk score, individual cardiovascular risks (tobacco use, lipids), health related quality of life and health care use. We will also assess the effects of the peer health coach intervention on intermediate outcomes including social support, patient activation, patient/provider communication and health behaviors (e.g. medication adherence, physical activity, nutrition, alcohol use, and stress management). In addition, we will assess the cost of the intervention to inform feasibility for future studies, determine Veteran and staff satisfaction with the intervention, and identify barriers and facilitators to adoption.

**IMPACT ON VETERANS HEALTH CARE:** Integrating peer health coaches into PACT primary care teams may improve the VA's ability to provide community outreach to Veterans. CVD risk reduction provides an ideal target for intervention given the prevalence of modifiable risks among Veterans. The proposed study will increase understanding of the utilization of peer support within PACT teams. If this study proves the main hypothesis, this evidence-based support model could be tested more widely among Veterans with other chronic conditions to improve health outcomes.

### List of Abbreviations

AHA	American Heart Association
ALVA	American Lake VA
AUDIT-C	Alcohol Use Disorders Identification Test
BMI	Body Mass Index
BRFSS	Behavioral Risk Factor Surveillance Survey
CAHPS	Consumer Assessment of Health Plans Study
CDW	Corporate Data Warehouse
CHW	Community Health Worker
CVA	Cardiovascular Accident
CVD	Cardiovascular Disease
DUA	Data Use Agreements
FFQ	Food Frequency Questionnaire
FRS	Framingham Risk Score
GIS	Geographic Information Systems
HLD	Hyperlipidemia
HPDP	Health Promotion and Disease Prevention
IHD	Ischemic Heart Disease
IPAQ	International Physical Activity Questionnaire
LDL-C	Low Density Lipoprotein
MOU	Memoranda of Understandings
MOVE	Weight Management Program for Veterans
OMHS	Office of Mental Health Services
PACE	Patient Aligned Care Team
PAM	Patient Activation Measure
PTSD	Post-traumatic stress disorder
PVD	Peripheral Vascular Disease
SBP	Systolic Blood Pressure
Vet-COACH	Veteran peer Coaches Optimizing and Advancing Cardiac Health
VFW	Veterans of Foreign Wars

## Protocol Title:

### 1.0 Study Personnel (KEY)

- Provide name, contact information, and affiliations/employee status for the following:

#### Collaborators (at other institutions, not covered under the VA IRB approval):

None

### 2.0 Introduction

- Provide scientific background and rationale for study.
- Include summary of gaps in current knowledge, relevant data, and how the study will add to existing knowledge.
- Include rationale for including or excluding certain populations – in particular vulnerable populations.

### **High prevalence and sub-optimal control of CVD risk factors among Veterans:**

Cardiovascular risk is a composite measure of several modifiable risk factors including hypertension, dyslipidemia, and tobacco use. Sedentary lifestyles, unhealthy diets, and increasing obesity rates will likely continue to increase rates of hypertension, dyslipidemia and CVD. Because of these trends, a 2020 American Heart Association (AHA) goal is the promotion of ideal cardiovascular health, defined as the presence of 4 health behaviors (non smoking, BMI  $\leq 25$  mg/kg, physical activity at goal level, and diet consistent with current guidelines) and the presence of at least 2 ideal health factors (untreated total cholesterol  $< 200$  mg/dl, untreated blood pressure  $< 120/80$  mmHg, or untreated fasting glucose  $< 100$  mg/dl). The majority of U.S. adults meet very few of these goals. Similar to the US population, Veterans have high rates of CVD risks. Almost half of Veterans seen in primary care have a hypertension diagnosis and one quarter have poor control. Veterans who obtain care from VHA are more likely to be obese and physically inactive than the general population and the prevalence of tobacco use among Veterans is 25%.

### **CVD risk factor control will require a multi-faceted intervention:**

Comprehensive approaches to control CVD risk will need to focus on multiple risk factors including blood pressure, high cholesterol, tobacco use, body-mass index, physical activity and nutrition. Control of hypertension and other modifiable CVD risks requires medication management in addition to behavioral interventions to change health behavior. National guidelines recommend that all individuals with hypertension undergo the following lifestyle modifications: loss of 5-10% of body weight, or maintain normal weight; moderate physical activity, change diet to be low sodium; smoking cessation and moderate alcohol consumption. Focusing on more than one of these aspects of healthy lifestyle is synergistic and can lead to greater improvements in hypertension control. Existing studies suggest significant benefit in blood pressure control from lifestyle modifications with a decrease in SBP from 5 - 20 mm Hg with 10 kg loss of body weight, a decrease in SBP from 8 - 14 mm Hg with dietary changes, a decrease of 4 - 9 mm Hg with regular physical activity and 2 - 4 mmHg with moderate alcohol consumption. Given the high rates of medication non-adherence among individuals with hypertension, focusing on this topic is critical.

### **Gaps in knowledge about peer support interventions among Veterans in primary care:**

Trained peers may be a novel and innovative addition to existing programs, as peers can be effective in supporting health behavior change and make healthcare more patient-centered. Peer support, defined as the provision of support and information from a member of a social group who possesses experiential knowledge and similar characteristics to the target population, falls into the social support model, where social relationships improve health-related quality of life and well-being. To date, peers have been utilized in several studies at VHA, including two studies that showed significant clinical improvement among patients with diabetes. Previous research in non-VA populations suggests that peer coaches working in conjunction with nurses are effective at controlling cardiovascular risk factors, but work is needed to determine how to integrate peer support into PACT teams to help assist Veterans. One component of the PACT initiative is the utilization of RN care managers to coordinate care. Care management provided by registered nurses can be effective, but is expensive. Veteran peer health coaches are a potentially more cost effective mechanism to increase outreach and link Veterans to their PACT team and RN care managers.

### **Peer support and the unique experiences of the Veteran community:**

The positive health benefits of peer support may be particularly strong in the Veteran community. Veterans have long organized into community organizations (e.g. VFWs) based on

their unique military experience, the powerful formative experiences of military service and unique post-discharge experiences (e.g. PTSD, integrating back into civilian life). Because of these common experiences, Veterans may find it easier to understand and accept the health recommendations of a peer health coach. Peer coaches may also be able to help Veterans and providers to understand each other's perspective and priorities. This shared experience has been utilized effectively in the treatment of Veterans with mental health conditions. The VHA Office of Mental Health Services (OMHS) has a well-developed peer support program and has hired 300 Veterans to assist mental health clinical teams. The core features of the recovery model for mental health (e.g. peer support, holistic orientation, self-direction, and patient-centeredness) are integral to most chronic disease self-management programs. However, the peer support approach has not received widespread testing among Veterans cared for in primary care. By leveraging the shared military experience and camaraderie of Veterans, the peer coach model may be an untapped opportunity to improve health among primary care patients and may work more effectively in the VA, but this model needs further testing..

#### **Contributions of the proposed work:**

CVD remains the number one cause of mortality among Veterans and sub-optimal risk factor control contributes to the ongoing prevalence of CVD. Our goal is to decrease CVD risk among Veterans by addressing modifiable risk factors (hypertension, elevated cholesterol, overweight/obesity and tobacco use) with an innovative, patient-centered intervention. Our approach to multiple risk reduction with a novel peer coach intervention mirrors clinical practice, where multiple conditions and behaviors are considered simultaneously. Peer support models have been utilized effectively in other patient populations to manage CVD risk and improve BP control, but limited work has been done within the context of the PACT team or in Veteran populations. The intervention will be integrated into primary care clinics and PACT teams at two clinical sites, enhancing the potential for benefit and generalizability to other settings. The intervention is consistent with the PACT goals to provide more longitudinal and less episodic care. The proposed intervention could potentially decrease CVD risk among Veterans by 1) building upon previous work with peer support among non-Veteran populations; 2) focusing on multiple synergistic CVD-related behaviors and risk factors and 3) targeting a high risk population (e.g. Veterans with 2 or more CVD risks) thereby providing the greatest potential to improve morbidity and mortality. Our proposal is innovative in the use of a hybrid type 1 design, which will inform future implementation efforts. The Vet-COACH intervention was designed with our clinical partners and is integrated into the PACT team. Given the national prevalence of CVD and the low rates of risk factor control, easily disseminated interventions such as the one proposed could significantly improve health outcomes.

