### Study design overview:

We propose a randomized controlled trial to evaluate the effectiveness of **Vet-COACH**, a peer health coach program to control hypertension and reduce CVD risk among Veterans. The original program incorporated home visits by peer health coaches to deliver health education, counseling and goal setting support. Due to safety concerns and social distancing restrictions stemming from the COVID 19 pandemic, the program has transitioned to conducting all health coaching encounters, as well as enrollment and exit visits, via phone. This transition was implemented under IRB approval of the miscellaneous memo submitted at the beginning of the pandemic. These changes to conduct all health coaching encounters and exit surveys over the phone will be permanent for the remainder of the study. Our operations partners from NCP have developed extensive patient educational materials that will be used for the current study. We will train the peer health coaches to provide brief educational messages and link Veterans to existing clinical services at VHA, including their primary care PACT teams and community based programs. The main outcome will be a reduction in systolic blood pressure. Secondary outcomes are cardiovascular risk, as measured by the Framingham Risk Score (FRS), health care utilization and intermediate behavioral outcomes including patient activation, social support and health behaviors (e.g. diet and physical activity, medication adherence). *We will randomize a total of 200 individuals to the intervention group and 200 individuals to the control group.*

Our study design has limitations. Because of the nature of the intervention, we are unable to blind treatment assignment. The PI and [name] will provide overall supervision to the peer coaches. This model is necessary for program development. Because the intervention is being conducted at two sites, we are not proposing an economic evaluation to estimate cost-effectiveness, in part because such data would be of limited generalizability. Positive findings will lead to a larger multi-site trial that would include a cost-effectiveness analysis. These limitations are more than balanced by the strengths of this proposal. The proposed project is a prospective, randomized controlled trial that examines important outcomes with statistical power to detect clinically meaningful differences.

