
**b) Randomization**

Following baseline assessments, a computerized randomization procedure will assign individuals to either the peer health coach intervention or to the usual care + education control group. Randomization of participants will occur in the order of completed enrollment visits. Randomization lists will be constructed in advance by the study biostatistician using variable

length blocks to ensure the groups are not unbalanced at any time. Concealment will be used to prevent the study staff from obtaining information on the sequence of assignment.

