## 5.2 Recruitment Methods

- State how many subjects will be needed.
- Describe when, where, how and by whom potential subjects will be identified and recruited.
- Describe materials that will be used to recruit subjects, e.g., advertisements. Include materials as an appendix or separate attachment. Only refer to attachments as A, B, etc. Do not refer to version #'s or dates of versions. During the course of the study, changes in the attachments will require IRB approval; however, those changes may not require a revised protocol.
- Describe any payments to subjects, including the amount, timing (at the end of the study or pro-rated for partial study participation), method (e.g., cash, check, gift card), and whether subjects will experience a delay in receiving the payment.

Eligibility for participation will be determined by identification of potential participants and Vet-Coachers from VA administrative data files from VA Corporate Data Warehouse, as well as the "Quality Improvement for Primary Care Clinic" project conducted through the Seattle VA Primary Care Clinic for relevant diagnostic and lab-based criteria. Census tract data from the Quality Improvement project will be linked to subject geographic data (address) in the VA administrative files. This information will be obtained by the project programmer. Using administrative data, we identified approximately 17,080 Veterans at VA Puget Sound (cared for at either the Seattle or American Lake Divisions) with hypertension, of whom n=2,955 have a systolic blood pressure that is > 150 mm Hg. Approximately 90% of this population is overweight or obese (a second criteria for entry into the study) (n=2,486). Our target sample size for recruitment is n=400. A letter from the study signed by the primary care provider (PCP) with an opt-out option will be

mailed to potential participants informing them of the project and encouraging participation. Project staff (project manager and research assistant) will then contact patients by telephone to assess eligibility and interest in participation and to arrange an enrollment visit.

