**N/A – We have 1 primary site.**

## 9.0 Information Security and Privacy

The principal investigator will review critical incidents (participant death and hospitalization). For each such event, [name] will evaluate the potential for causal relations between the incident and study or intervention procedures. Any adverse effects of the study will be reported to the participant and his/her health care provider. Major adverse events requiring hospitalization will be reported to

the study project manager and the IRB. [name] will be available to meet with the participant and provider to discuss any concerns. The participants will bear no financial risk from any adverse effects of encounters from this study. Including only numeric identifiers on all data collection instruments will protect confidentiality of collected information. Code keys and data collection documents (when not in use) will be kept in a locked file or password-protected terminals.

Several steps will be taken to minimize the risk of invasion of privacy. Initial contact with prospective participants will be made via an introductory letter with a stamped post card allowing her/him to opt out of further contact by the study team thus limiting risk for invasion of privacy. A number of steps will be taken to ensure confidentiality and data protection throughout the rest of the study. All data gathered at the enrollment visit (the questionnaire, physical exam, health goals) and subsequent information will be confidential. Data will be kept in offices at VA Puget Sound HSR&D with locked filing cabinets and password protected computers. The investigators, project coordinator, and study staff will be the only staff to have access to confidential records. ID numbers rather than names will be used whenever possible. As part of the study, individuals will be reassured that information is to be kept confidential, no single individual will be identified by name and all data will be aggregated. All data files will be maintained on password protected PCs and password protected computer networks. Only aggregate data will be presented to external audiences. Individual identifiers will be deleted when they are no longer necessary for the project.

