6. STATISTICAL ANALYSES AND DESCRIPTION OF MAIN TABLES

The primary outcomes are changes from baseline to one year in systolic blood pressure. We will test the primary hypothesis that among Veterans with poorly controlled hypertension and at least one other CVD risk, the **Vet-COACH** intervention targeting behavior change and disease self-management will decrease SBP by 4 mmHg compared to a usual care + education control group. Primary analyses will be conducted on an intent-to-treat basis; participants will be analyzed in the group to which they were assigned, regardless of intervention adherence, using all follow-up data or up to last available measurement prior to exclusion or dropout.

Primary Effectiveness Analyses for Specific Aims 1 & 2

Since there are multiple patients enrolled per physician and multiple patients enrolled per peer health coach, a physician-level and peer health coach random effect will be included in the primary analytic model to take this correlation into account. For the Aim 1 primary outcome analysis, we will evaluate change in systolic blood pressure, from baseline to 12 months, in the intervention versus controls using the following random effects model:

$$Y_{ij} = \mu + \beta_1 \text{Group}_{ij} + \beta_2 \text{Baseline}_{ij} + \beta_3 x_{ij} + \alpha_j + \text{Group}_{ij} * \tau_k + \epsilon_{ijk}$$

where Y_{ij} is the change in blood pressure from baseline to 12 months for subject i having provider j (and k for peer coach intervention participants); μ is the overall mean; Group_{ij} is group assignment (intervention vs. control); Baseline_{ij} is the baseline BP value; x_{ij} are baseline covariates that could affect the outcome; α_j is the random effect for provider cluster j and τ_k is the random effect for peer coach cluster k (note that τ_k is multiplied by the intervention indicator Group_{ij} so that the added peer coach correlation is accounted for only amongst intervention participants, as suggest by Roberts et al). Our main goal is to test whether $\beta_1 = 0$ which is the difference in BP change (from baseline to 12 months) between the intervention and control groups.

The main conclusions drawn from this trial will be based on the pre-specified primary hypothesis tested with two-sided p-values at the standard 0.05 level with associated effect size differences and confidence intervals.

MAIN ANALYSIS:

Unadjusted

Secondary: Prespecified variables will include sex, age, and race

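### Two clinical sites, but no site stratification and no site term in the primary SBP model: a modest, avoidable loss of precision if coaches work mainly at one site

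*Protocol*

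**What the plan says.** **Sites.** The protocol's introduction says "The intervention will be integrated into primary care clinics and PACT teams at two clinical sites". The study design overview repeats the count when it rules out a cost-effectiveness analysis ("Because the intervention is being conducted at two sites"). Section 5.2 describes the source population as Veterans "cared for at either the Seattle or American Lake Divisions". The entry that closes section 8.0 (Communication Plan) reads "We have 1 primary site". It answers a template item on coordinating multi-site studies and does not remove the two clinics, but the wording should be reconciled.

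**Randomisation.** Lists use variable-length blocks, and "Randomization of participants will occur in the order of completed enrollment visits". Neither the protocol nor SAP section 1 names a stratification factor.

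**Model.** SAP section 6 says "a physician-level and peer health coach random effect will be included in the primary analytic model", with the coach effect acting in the intervention arm only. The fixed part holds group, baseline BP and unspecified baseline covariates. The SAP labels the main analysis as unadjusted and then adds "Secondary: Prespecified variables will include sex, age, and race". Site is in neither the protocol's covariate list (section 5.5) nor the SAP's (section 5).

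**Coaches.** The power section assumes 5 coaches with 35 patients each. Neither document says whether coaches are assigned by site.

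**The concern.** The two random effects treat an omitted site difference differently. Both arms share the provider effect, so site variance absorbed there largely cancels from the treatment contrast. The coach effect exists only in the intervention arm, so whatever it absorbs goes straight into the standard error of the contrast.

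If each coach works at one site, a site difference in SBP change looks like a difference between coaches. The model then charges it as uncertainty about the intervention, although both arms enrol at both sites and the difference is not treatment noise. With about 5 coaches the effect on the interval can be visible. At stake are the width of the confidence interval for the primary contrast and some power.

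**Working it through.** **1. The plan's own sample size.** Inputs from Protocol section 5.6: difference 5 mmHg, SD 14.2, power 80%, alpha 0.05 (two-sided per SAP section 6), provider ICC 0.015 with clusters of 5, coach ICC 0.007 with clusters of 35, attrition 15%.
- Per arm, no clustering: 2 × (1.960 + 0.842)² × 14.2² / 5² = 126.6.
- Design effect, control: 1 + 4 × 0.015 = 1.06.
- Design effect, intervention: 1.06 × (1 + 34 × 0.007) = 1.06 × 1.238 = 1.312.
- Mean design effect: (1.06 + 1.312) / 2 = 1.186.
- Evaluable: 2 × 126.6 × 1.186 = 300.4. Enrolled: 300.4 / 0.85 = 353.4, against 354 stated.

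The figure reproduces and has no separate site component.

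**2. How large a site difference fits the plan.** Provider variance is 0.015 × 14.2² = 3.02 mmHg². A site difference d with site shares p and 1 − p contributes d² × p(1 − p). If the provider ICC already includes site, d is at most √(3.02 / 0.25) = 3.5 mmHg for equal sites, and √(3.02 / 0.24) = 3.5 mmHg for a 60/40 split.

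**3. Simulation of the SAP model.** Settings from the plan: 5 patients per provider, 70 providers, 5 coaches in the intervention arm, the two ICCs, total SD 14.2, true effect 5 mmHg. Analysis by REML with intervals of ±1.96 SE, 1,500 replicates, unstratified variable blocks. Each dataset was fitted with and without a fixed site term. Assumed, because the documents do not give them: the site difference, a 60/40 site split, and how coaches are assigned. No baseline covariate was simulated. For differences up to 3.5 mmHg the site variance was taken out of the 3.02; the 6 mmHg rows add it on top.

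| Coaches | Site difference (mmHg) | SE without / with site | SE ratio | Power without / with site |
|---|---|---|---|---|
| One site each | 0 | 1.657 / 1.672 | 0.991 | 85.3% / 84.7% |
| One site each | 1.5 | 1.681 / 1.670 | 1.007 | 84.6% / 84.7% |
| One site each | 3 | 1.756 / 1.664 | 1.055 | 82.5% / 84.8% |
| One site each | 3.5 | 1.793 / 1.661 | 1.079 | 81.7% / 84.6% |
| One site each | 6 (beyond the ICC) | 2.058 / 1.672 | 1.231 | 71.3% / 84.7% |
| Both sites | 3 | 1.657 / 1.652 | 1.003 | 85.0% / 85.4% |
| Both sites | 6 (beyond the ICC) | 1.683 / 1.659 | 1.014 | 83.4% / 85.0% |

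With 60 providers (300 evaluable) and site-based coaches, power without and with the term is 77.7% / 81.3% at 3 mmHg and 68.1% / 81.0% at 6 mmHg.

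**4. Mechanism and bias.** With site-based coaches and no site term, the mean estimated coach variance rises from 2.6 mmHg² at no site difference to 4.5 at 3 mmHg and 10.4 at 6 mmHg. The empirical SD of the estimate barely moves (1.55 to 1.57), so the extra width is not real sampling error. The mean error of the estimate is at most 0.06 mmHg in every setting.

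**5. Stratification alone.** With site-stratified blocks but no site term, the SE is still 5.8% (3 mmHg) and 23.5% (6 mmHg) wider than with the term.

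**The case against.** - **Site-based coaching is an assumption.** Coaching is now permanently by phone, and study meetings run through one VA Puget Sound office. Candidate coaches came from a project at the Seattle clinic. In the other direction, the programme began with home visits, enrolment began in 2017 before the move to phone, and the same coach stays with a participant throughout. The documents settle neither side, so the point stands as a conditional one.
- **The coach ICC may already include site.** Coach variance is 0.007 × 14.2² = 1.41 mmHg². With site-based coaches and equal sites this caps the difference at √(1.41 / 0.25) = 2.4 mmHg, where the loss is smaller than in the 3 mmHg row. This is fair, and it is why the lower end of the range is close to nil.
- **The planned 80% is still met.** This is true with 350 evaluable patients at up to 3.5 mmHg. It is not true at 3 mmHg with the 300 evaluable that underlie the stated 354. The 200 per arm less 15% would leave 340.
- **Nothing shows that the sites differ.** They are divisions of one system, and baseline BP and provider are in the model. This is also fair; the case for a site term rests on its low cost.
- **There may be more than 5 coaches.** The interview plan allows for up to eight. In a separate simulation with 8 coaches, a 5 mmHg difference inflated the SE by about 10% with little change in power.
- **The open covariate term could hold site.** The equation permits it, but the SAP calls the main analysis unadjusted and names only sex, age and race for the secondary one.

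Two stronger readings are tempting. A reader might infer that omitting site biases the effect or inflates type I error. It does neither: the interval is, if anything, conservative. Chance imbalance is also minor. With 170 per arm, the difference in site share has SD √(2 × 0.25 / 170) = 0.054, so a 3 mmHg site difference moves the contrast by about 0.16 mmHg against an SE near 1.7. A reader might also infer that power falls to about 70%. That needs a site difference of 5 to 6 mmHg added to the plan's variances. At 5 mmHg with equal sites this is 25 × 0.25 = 6.25 mmHg² on top of a provider variance of 3.02, and the documents give no ground for it.

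**Conclusion.** The point holds as one of efficiency. Two sites enrol, and neither the randomisation nor the primary model accounts for site. If coaches are site-based, there are 5 of them, and the site difference is 3 to 3.5 mmHg, the interval is about 5-8% too wide and power about 2-3 points lower. At 300 evaluable patients and 3 mmHg, power drops from about 81% to 78%. At 1.5 mmHg the loss is negligible. If coaches serve both sites, the SE is 0.3-1.4% wider and the loss at most about 2 points, even at 6 mmHg. The validity of the primary test is not in question. The change is worth making because it costs little and removes the dependence on how coaches were assigned.

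**What to change.** In SAP section 6, add site (Seattle or American Lake, as recorded at enrolment) as a fixed effect in the primary SBP model and in the secondary and intermediate outcome models. Keep the provider and coach random effects. Amend the unadjusted label of the main analysis so that it states the site term.

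Settle this before outcomes are seen by arm; otherwise report the site-adjusted model as a sensitivity analysis. Check the coach assignment records and state whether coaches worked at one site or both. Reconcile the one-site entry in Protocol section 8.0 with the two-site statements. A descriptive SBP effect by site is optional.

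The cost is one line of text and 1 degree of freedom, about 1% in SE if the sites do not differ (1.672 against 1.657). Division should be available from the administrative data used to identify participants. Randomisation need not change: stratified blocks without the model term would not have removed the problem.
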